3.1.3 Cycle B – Virtually-Based Efficacy Study

In the second year (after the completion of Cycle A), a virtually-based efficacy trial will be conducted by CHOP staff via videoconference. Subjects will be randomized to the VR intervention or to the treatment-as-usual condition (with stratification, see *Study Procedure*). Subjects in each condition will undergo a baseline assessment of police interaction skills via a novel pre-/post-intervention assessment and three sessions within an approximately six-week period. At the end of Visit 3, subjects' police interaction skills will be assessed. There will be an additional follow-up visit approximately 4 weeks post-training, for all participants, to readminister outcome measures, as an assessment of maintenance of learning.

3.2 Study Duration, Enrollment and Number of Sites

3.2.1 Duration of Study Participation

In the first year of the study (Cycle A), the study duration per subject will be up to 3 visits over approximately 6 weeks. In Cycle B, the study duration per subject will be up to 4 virtual sessions over approximately 10 weeks.

3.2.2 Total Number of Study Sites/Total Number of Subjects Projected

The study will be conducted at approximately two investigative sites in the United States. Cycle A of the study will be conducted at the Center for Autism Research at CHOP, while Cycle B will be conducted virtually using CHOP approved, HIPPA compliant video conferencing software.

Recruitment will stop when approximately 48 evaluable subjects complete each phase of the study. It is expected that approximately 400 subjects will be enrolled to produce 96 evaluable subjects.

3.3 Study Population

3.3.1 Inclusion Criteria

- 1) Males or females age 12 to 60 years
- 2) Documented ASD diagnosis
- 3) Verbal and overall IQ \geq 75 (Cycle A)/Verbal and overall IQ \geq 80 (Cycle B)
- 4) Informed consent (if adult) or parental/guardian permission (if child or adult with diminished capacity) and, if applicable, assent

3.3.2 Exclusion Criteria

- 1) Participation in Phase I (IRB# 14194)
- 2) Personal or family history of seizures or a seizure disorder, subject to review on a case by case basis by medical professionals at Floreo
- 3) Primary sensory impairment (e.g., blindness, deafness)
- 4) Personal history of migraines, subject to review on a case by case basis by medical professionals at Floreo
- 5) History of vertigo
- 6) Diagnosis of a known genetic syndrome (e.g., Down syndrome, Fragile X syndrome)
- 7) History of a medical condition which has affected/affects cognitive, sensory, or motor functioning (e.g., Fetal Alcohol Syndrome, brain injury, stroke, brain tumor)
- 8) Non-English speaking

9) Parents/guardians or subjects who, in the opinion of the Investigator, may be non-compliant with study schedules or procedures

Subjects that do not meet all of the enrollment criteria may not be enrolled. Any violations of these criteria must be reported in accordance with IRB Policies and Procedures.

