9.4.2 Risk Assessment

Psychological Stress and Anxiety. Due to the time associated with conducting the assessments, some subjects may experience fatigue, anxiety, or stress. The Baseline Assessment and live police interactions may also produce these feelings. Subjects will be allowed to take breaks and stop at any time.

The study visits will be organized to involve breaks for the subject, and to allow the subject to rest between procedures. Experienced clinicians will always be available to help in efforts to reduce anxiety. Research staff working on the project all have experience working with adolescents and adults, and the PI and co-Investigators each have extensive experience working with individuals with ASD, and will therefore do everything possible to accommodate subjects.

Risk of Seizures and Migraines. There is a very low risk of seizures as a result of Virtual Reality technology, which is significantly increased for individuals with a history of seizures. There is also a low risk of migraines, which is significantly increased for individuals with a history of migraines. To reduce both of these risks we will screen all subjects for both a personal and family history of seizures and a personal history of migraines, and exclude any subject who

screens positive for either personal or family history of seizure activity of any type or personal history of any degree or migraines.

There is also some evidence that sleep deprivation and recent alcohol use may increase risk for seizure activity during use of Virtual Reality or other technologies. Therefore, we will encourage participants to reschedule in the event of night-before sleep deprivation or recent alcohol use, to avoid testing on days with either of these risks present. Finally, there is some evidence that extended playing time is associated with increased seizure risk. Therefore, we include required breaks between trials in the Virtual Reality intervention, with approximately 20 minutes of VR and 20 to 25 minutes of break time during the 45 minute VR intervention condition.

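### Section 3.3.2 lets subjects with a seizure or migraine history be considered for entry after review at Floreo, although 9.4.2 gives exclusion of every such subject as the safeguard

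*Combined protocol and SAP*

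**What the plan says.** Two of the nine exclusion criteria in 3.3.2 carry a review clause. Item 2 is "Personal or family history of seizures or a seizure disorder, subject to review on a case by case basis by medical professionals at Floreo". Item 4 is "Personal history of migraines, subject to review on a case by case basis by medical professionals at Floreo". Sections 1.1 and 1.2 identify Floreo as a commercial company and the police safety module as its product.

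Section 9.4.2 addresses the same histories as a risk-reduction measure. The stated measure is to "screen all subjects for both a personal and family history of seizures and a personal history of migraines, and exclude any subject who" meets a set condition, and the condition is worded as "screens positive for either personal or family history of seizure activity of any type or personal history of any degree or migraines". No review step or exception is mentioned. The section gives its reason: VR carries a "very low risk of seizures as a result of Virtual Reality technology, which is significantly increased for individuals with a history of seizures", and likewise a "low risk of migraines, which is significantly increased for individuals with a history of migraines".

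Section 9.4.4 then rates all study procedures as minimal risk. Section 8.1 classes any seizure triggered during participation as a serious adverse event. The age range in 3.3.1 starts at 12.

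**The concern.** A reader of 9.4.2 would conclude that nobody with a personal or family seizure history, or a personal migraine history, is ever put in the headset. A reader of 3.3.2 would conclude that such a person may be considered, depending on a review by the developer's medical staff. The risk section thus describes a tighter safeguard than the entry rule delivers, and the minimal-risk rating follows from that description.

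The protocol also leaves open who decides after the review. It names no standard for the decision and no decision-maker. The only medical review described is by staff of the company whose product is being tested. What is at stake is the protection of subjects, some of them minors, and the accuracy of the risk description. The efficacy estimate is not at issue.

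**Working it through.** There is no figure to reproduce, so the check compares the two sections as they would apply to one subject and then looks elsewhere in the protocol for text that reconciles them.

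1. **Same histories in both places.** Item 2 covers personal or family seizure history, and 9.4.2 covers personal or family seizure activity. Item 4 covers personal migraine history, and so does 9.4.2. The scope matches.

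2. **Different rule.** Take a subject with a past migraine.
   - Under 3.3.2 item 4, the subject is excluded unless review allows otherwise.
   - Under 9.4.2, the subject is excluded. The wording "screens positive for either personal or family history of seizure activity of any type or personal history of any degree or migraines" leaves no grade of severity for a reviewer to weigh.

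3. **The clause must allow admission to have any purpose.** If every positive screen were excluded whatever the review found, there would be nothing to review. Vertigo (item 5 of the same list) is excluded with no such clause, so the qualifier on items 2 and 4 looks deliberate.

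4. **Search for a decision-maker.**
   - Sections 3.1.1, 4.1 and 9.6 describe screening. In 9.6 study staff tell the subject whether and why they are eligible, but nothing says who rules on an exception.
   - Item 9 of 3.3.2 uses the Investigator's opinion, but for likely non-compliance.
   - The clinicians in 9.4.2 are there to help reduce anxiety, and the study clinician in 5.1.3 and 9.4.3 is involved in feedback.
   - Section 9.4.1 establishes a monitoring board but gives it no eligibility role. Its charter is not among the documents.

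5. **Who is exposed.** In Cycle A the headset is used in the VR arm only, because the comparator is video-based and the assessments are live. In Cycle B both arms are exposed: 5.3.2 has control subjects use the software for assessments, 5.4.1.2 has all participants wear the headset at baseline, and 5.4.2.2 uses it again afterwards.

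6. **Extent.** Items 2 and 4 are 2 of 9 exclusion criteria. The protocol gives no number of cases expected to be reviewed or admitted, so no count of affected subjects can be derived.

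**The case against.** The strongest reply is that the clause obliges nobody to admit anyone. If no exception is ever granted, both sections are satisfied. That is right, and a reader who infers that the two sections cannot both be followed goes too far. The conflict arises when a reviewed subject is entered.

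A reader might also infer that Floreo controls entry. The text gives its medical professionals a review and does not say that they make the final decision. The supported criticism is that the decision-maker is unstated.

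It is tempting to add that the protocol leaves unclear whether such an entry must be reported. The sentence in 3.3.2 is "Any violations of these criteria must be reported in accordance with IRB Policies and Procedures", and a subject admitted through the review that the list itself provides for does not violate that list. Departures from the rest of the protocol fall under 1.4, which requires noncompliance to be documented.

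The other safeguards are real. Health status is screened in every arm of both cycles (5.2, 5.3.1, 5.3.2), and eligibility is checked again at Visit 1 (Table 1). For VR use, "we include required breaks between trials in the Virtual Reality intervention" is one measure among several in 9.4.2. Subjects are asked how they feel between trials, sessions stop on nausea or eye strain, and rescheduling is encouraged after poor sleep or recent alcohol use. Section 9.4.1 adds follow-up after a first adverse effect. These lower the risk, but they do not reconcile the entry rule with the exclusion that 9.4.2 describes.

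Finally, 9.4.2 does not say that family history alone raises the risk, so admitting such a subject cannot be called hazardous on the documents.

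**Conclusion.** The point holds as an inconsistency in a safety rule: 3.3.2 items 2 and 4 permit what 9.4.2 rules out, and nothing else in the protocol resolves it. The mitigation described is stricter than the entry rule whenever a reviewed subject is admitted, and in Cycle B that matters for both arms.

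Its size is 2 of 9 criteria and an unstated number of subjects. The conclusion rests on one reading, that subject to review means admission is possible, which the unqualified vertigo exclusion supports. The screening questionnaire and the monitoring board's charter are not in the documents and may describe a process, but they would not change the wording of either section. A reader might infer inflated adverse event rates or a biased comparison between arms. The documents give no basis for either, and neither is claimed. The sponsor should correct this, and it is cheap to do so.

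**What to change.** Delete the review clause (everything after the comma) from items 2 and 4 of 3.3.2, so that the entry rule delivers the exclusion that 9.4.2 states.

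This is a wording change with one real cost. A few subjects who might have been admitted become ineligible, including those with only a family seizure history, for whom 9.4.2 states no increased risk. Their number is not stated. They would have to be replaced, but the planned evaluable number does not fall, because 3.2.2 continues recruitment until about 48 evaluable subjects complete each phase.

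If the sponsor prefers to keep the exception, two changes are needed:

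- **9.4.2:** state that subjects with these histories may be admitted after review, so that the risk description is accurate.
- **3.3.2 items 2 and 4:** state that the Investigator, not Floreo, makes the final decision, before randomisation and before any VR exposure. Floreo's medical staff may still advise. In Cycle B, VR exposure includes the baseline assessment in both arms. The decision must precede randomisation because 6.3.2 keeps every subject randomised at Visit 1 in the primary analysis.

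This alternative costs wording in two sections and some Investigator time.

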4 STUDY PROCEDURES

4.1 Screening Interview

- Informed Consent
- Screening Questionnaire
- Medical or Research Record Review

4.2 Characterization Visits

- Informed Consent, and assent if appropriate
- IQ testing (completed at first visit)
- ASD diagnostic testing (completed at any of the 3 intervention study visits in Cycle A only)
- Self-report measures
- Parent-report questionnaires
- Stratified randomization to either the VR intervention or to the video modeling control condition
- Medical or Research Record Review

4.3 Intervention Visits

- Baseline Assessment
- VR or video modeling session
- Pre and post-intervention Police Knowledge Assessment
- Police Interaction Assessment at the end of Visit 3
- Floreo Feedback Questionnaire following the Police Interaction Assessment (Cycle B)
- Debriefing

4.4 Follow-Up Visits

4.4.1 4 weeks post-intervention (Cycle B only)

- Police Interaction Assessment
- Police Knowledge Assessment
- Debriefing

4.5 Unscheduled Visits

No unscheduled visits are anticipated.

4.6 Subject Completion/Withdrawal

Subjects may withdraw from the study at any time without prejudice to their care. They may also be discontinued from the study at the discretion of the Investigator for lack of adherence to study visit schedules or procedures. The Investigator may also withdraw subjects who violate the study plan, or to protect the subject for reasons of safety or for administrative reasons. It will be documented whether or not each subject completes the pilot study. If the Investigator becomes aware of any serious, related adverse events after the subject completes or withdraws from the study, they will be recorded in the source documents and on the CRF.

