5.6 Safety Evaluation

Immediately after completing each intervention session, research staff will ask subjects about any side effects experienced during the session. Research staff will also document the subject's overall perceived mood and emotional state.

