6.3.3 Safety Analysis

All subjects entered into the study at Visit 1 will be included in the safety analysis. The frequencies of AEs by type, body system, severity and relationship to study intervention type will be summarized. SAEs (if any) will be described in detail.

AE incidence will be summarized along with the corresponding exact binomial 95% two-sided confidence intervals.

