8 SAFETY MANAGEMENT

8.1 Clinical Adverse Events

Clinical adverse events (AEs) will be monitored throughout the study. The PI and the research team will work together to minimize minor adverse events. This will be accomplished through systematic assessment for adverse events through active clinical observation and post-session

questionnaires. If adverse events occur, we will solicit direct guidance and feedback from CHOP's IRB, and immediately implement safeguards to decrease or eliminate future risks. Minor AEs that are unrelated to study participation will be reported to CHOP's IRB and the NIH program officer in a quarterly report.

Safety research on Virtual Reality (VR) indicates that photosensitive seizures, headache, and vertigo are adverse events possibly related to VR use. Our study team will consider new onset seizure disorder, any seizure triggered during participation, and either headache or vertigo severe enough to result in an emergency room evaluation or hospitalization to be SAEs and respond accordingly.

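### No active adverse-event query is set after the last Cycle A session, and none is expressly listed at the Cycle B 4-week visit, so AE incidence is likely understated for delayed effects

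*Combined protocol and SAP*

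**What the plan says.** Section 5.6 sets the one scheduled query: "Immediately after completing each intervention session, research staff will ask subjects about any side effects experienced during the session". Section 8.1 states that "Clinical adverse events (AEs) will be monitored throughout the study" and gives the means as "systematic assessment for adverse events through active clinical observation and post-session" questionnaires. It also lists what the team will treat as serious: "new onset seizure disorder, any seizure triggered during participation, and either headache or vertigo severe enough to result in an emergency room evaluation" or hospitalization. Section 9.4.2 adds migraine as a low risk of the technology.

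Section 4.6 governs the time after a subject finishes or leaves. "If the Investigator becomes aware of any serious, related adverse events after the subject completes or withdraws from the study", then "they will be recorded in the source documents and on the CRF".

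For the analysis, section 6.3.3 takes everyone entered at Visit 1, and "AE incidence will be summarized along with the corresponding exact binomial 95% two-sided confidence intervals". No section says for how long after a session an event still counts.

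**The concern.** Some of the effects the plan itself names tend to show themselves after the subject has gone home. An emergency visit for headache, a new seizure diagnosis or an evening migraine cannot be fully seen by a question asked as the headset comes off. If nobody asks later, the record holds only what families volunteer and what passes the section 4.6 filter.

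That filter has three conditions: the event must be serious, it must be related, and the Investigator must hear of it. During participation the plan is broader. Section 6.3.3 tabulates AEs by severity and relationship, and section 8.1 even reports minor unrelated events. The standard therefore narrows just when the last exposure's delayed effects would appear. It narrows at withdrawal too, so a subject who leaves after an unpleasant session moves straight to the restricted rule.

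At stake is the meaning of the AE incidence. A low figure with an exact interval would read as covering all effects of the module, when it mostly covers those seen or reported at the session.

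**Working it through.** The plan states no figure on this point, so there is none to reproduce. The check is mainly a comparison of sections, followed by a short calculation for scale.

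**Step 1. Who is asked what, and when**

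| Period | Active AE query | Recording rule |
|---|---|---|
| During and just after each intervention session | Yes (5.6, 8.1) | All AEs |
| Between sessions | None named; a health-status screen precedes each session (5.2, 5.3.1, 5.3.2) | All AEs, under the 8.1 monitoring statement |
| After Visit 3, Cycle A | None; follow-up visits are for Cycle B only (4.4.1) and no unscheduled visits are anticipated (4.5) | Serious and related and known (4.6) |
| Visit 3 to the 4-week visit, Cycle B | None expressly listed (4.4.1) | All AEs, under the 8.1 monitoring statement |
| After the 4-week visit, Cycle B | None | Serious and related and known (4.6) |

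**Step 2. Time from last exposure to end of participation**

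- Cycle A: the last session and the final assessment are both at Visit 3 (3.1.2), so 0 days.
- Cycle B: about 4 weeks from the last training session (3.1.3). But the 4-week visit repeats the virtual assessment with the headset on (5.4.2.2), and control subjects also use the software for assessments (5.3.2). Counted from the last headset use, the time is again 0 days, in both arms.

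**Step 3. Which delayed events fall out after completion or withdrawal**

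- A migraine that does not lead to an emergency visit or admission is not serious under 8.1, so 4.6 does not call for it to be recorded.
- A serious event judged unrelated is likewise outside 4.6.
- New-onset seizure disorder and emergency- or hospital-level headache or vertigo are serious by definition. If judged related and known, they are recorded. Their capture depends on passive reporting and on the relatedness judgement.

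**Step 4. Direction**

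The denominator is fixed as all subjects entered at Visit 1 (6.3.3). A missed event can only leave the numerator unchanged or lower it, so any error in incidence from this source is downward.

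**Step 5. Scale, for illustration**

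Section 6.4 gives 48 subjects per study. An equal split gives 48 / 2 = 24 per arm. This is an assumption: no allocation ratio is stated, and the safety set may be larger than the evaluable number.

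- Exact two-sided 95% upper limit for 0 events in n: 1 − 0.025^(1/n). For n = 24 this is 14.2%; for n = 48 it is 7.4%.
- Exact interval for 1/24: 0.1% to 21.1%.
- One missed event in an arm of 24 therefore changes the report from 1/24 = 4.2% (0.1% to 21.1%) to 0/24 = 0% (0% to 14.2%).
- Chance that at least one of 24 subjects has a delayed event: 1 − (1 − p)^24. The documents give no p. For assumed values of 1%, 3%, 5% and 10%, the results are 21%, 52%, 71% and 92%.

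The last line shows why no size can be given: the answer runs from unlikely to near certain, depending wholly on the assumed rate.

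**The case against.** The case for leaving the plan alone has real parts.

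- **Monitoring is study-wide.** Section 8.1 says so, and in Cycle B that covers about 4 weeks after training. This stands. A reader might infer that AE collection closes on the day of the last session; no section says that, and for Cycle B it would be wrong. But the statement gives a period without a method, and in Cycle A the period ends at Visit 3.
- **The gravest events are covered.** A reader might also infer that delayed seizures or emergency-level headache and vertigo go uncounted. The documents do not support this: section 4.6 has them recorded if related and known, and section 6.3.3 describes SAEs in detail. The weakness is how they come to be known.
- **Visit lists are not complete on safety.** The intervention-visit list in 4.3 has no AE item either, yet 5.6 requires a query there. Table 1 appears to mark a virtual reality session at Cycle B Visit 4, and 4.4.1 includes a debriefing. So a query may be intended at that visit. It is not expressly stated, though, and the 5.6 wording would cover only effects of that day's session.
- **Other routes exist.** The pre-session health screen can pick up effects of sessions 1 and 2, though it is described as preparation and cannot reach the last session. Families have staff contact details (9.6), section 4.6 does not forbid recording more than it requires, and section 8.2 has notable non-serious AEs summarized for the IRB. These help, but all of the routes after the last session depend on someone volunteering information.
- **Safety is not the focus here.** Section 2 says safety was acceptable under a separate protocol, safety is neither a primary nor a secondary endpoint, and the risks are rated minimal (9.4.4). This limits the weight of the point. It does not remove it, because 6.3.3 still plans an incidence with intervals, and section 2 says the module will become more complex.

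The post-session questionnaires and the DSMB charter are not in the documents and might add something.

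**Conclusion.** The point holds in a limited form. No AE window is stated. No active query follows the last Cycle A session, and none is expressly listed at the Cycle B 4-week visit. After completion or withdrawal, non-serious events and events judged unrelated fall outside the recording rule, while delayed SAEs depend on passive reporting and a relatedness judgement. Incidence under 6.3.3 is therefore likely understated for delayed effects.

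The direction follows from the sections themselves. It requires only that some delayed events occur and are not volunteered. The size cannot be estimated: the one-event comparison rests on an assumed 24 per arm, and the 1% to 10% rates are illustrative. It would be going too far to say that delayed events cannot enter the numerator, or to attach a percentage to the shortfall. The efficacy analysis is untouched. This is a cheap improvement.

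**What to change.** - In 4.6 and 5.6, define an AE collection window that runs a fixed period, chosen by the sponsor, past the last session or headset use. Make it the same in both arms. In Cycle B this also settles how control subjects, who use the software only for assessments, are asked.
- Record all AEs within the window, whatever their seriousness or relatedness, including for subjects who withdraw. The present 4.6 rule can apply after the window closes.
- At the start of each later visit, including the Cycle B 4-week visit, ask about symptoms or medical visits since the last visit, and add the item to 4.3, 4.4.1 and Table 1.
- Send one short REDCap survey, or make one call, after the final visit of each cycle.
- In 6.3.3, state that AE incidence refers to this window.

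The cost is protocol wording, one question per later visit and one brief extra contact per subject on a platform already in use. Reported AE rates may rise slightly. No treatment, endpoint or sample size changes.
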